An alternative hypothesis that could explain stimulation effects on cognition concerns the frequency of stimulation. The optimal benefit for motor function occurs with high frequency stimulation, on the order of 130 Hz, although there is some minor variation across patients. Stimulation at this frequency appears to interrupt the pathological beta oscillations that occur in the basal ganglia associated with motor impairments. LFP recording in PD patients suggests that oscillatory activity is important for cognitive function⁸ and high frequency stimulation may interfere with cognitive processing. This fits with Wojtecki and colleagues⁹ finding that verbal fluency performance worsens with high frequency stimulation and improves with low frequency stimulation.

This study will clarify prior observations of cognitive changes in patients with STN DBS²⁷ and opens the door to tailoring stimulation parameters to independently influence cognitive or motor function. For example, DBS technology could be designed to improve both cognitive and motor symptoms by stimulating at one frequency in dorsal STN, and another frequency in ventral STN.

Aim 1. To evaluate the cognitive effects of high frequency stimulation at dorsal and ventral contact locations in PD patients with bilateral subthalamic nucleus DBS electrodes. We hypothesize that, relative to OFF stimulation, performance on tasks involving executive functions will show greater change at ventral contacts than at dorsal contacts.

Aim 2. To evaluate the cognitive effects of low frequency stimulation at dorsal and ventral contact locations in PD patients with bilateral subthalamic nucleus DBS electrodes. We hypothesize that, for tasks where high frequency stimulation produces a *deficit* relative to OFF stimulation (e.g., verbal fluency), low frequency stimulation will *eliminate or reverse* performance changes relative to OFF stimulation.

Aim 3. To characterize changes in cognitive network activity during alternative stimulation of the STN. We will also collect scalp EEG data during task performance when stimulation is OFF compared to alternative DBS settings. Patients with Medtronic or Abbott/St. Jude DBS systems that have been MRI safety tested will also undergo fMRI on a second day to examine BOLD

responses during task performance while stimulation is OFF compared to alternative DBS settings.

Study Design

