Test sessions: Controls will complete five 25-minute testing sessions separated by 10-15 minute break periods. Each session will involve performance of several tasks that may include phonemic fluency, semantic fluency, Simon task, Facial Affect Recognition task (FAR), or Interval Judgment task.

Data Analysis

Behavioral Tasks: With the support of a Biostatistics consultant (_____), we propose to evaluate the behavioral task data using a combination of methods for General Linear model and categorical data methods where appropriate. Selected details are presented with the relevant aims above. Statistical corrections will be applied to avoid any increase in family-wise error rate.

EEG: We will analyze event-related potentials (ERP) to trial events in individual tasks to investigate phase-locked activity. Non-phase-locked activity will be investigated by averaging power within alpha, beta, and gamma frequency bands with respect to the trial events. The latter analysis technique will permit identification of event-related desynchronizations (ERD) and synchronizations (ERS)²⁴ associated with non-clinical stimulation parameters.

BOLD: Event-related functional MRI data at all stimulation settings will be analyzed for individual subjects to evaluate patient-specific changes in activated networks. Group-level analyses will be dependent on the degree of similarity across patients in terms of specific cognitive performance changes and associated stimulation parameters.

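### The EEG plan labels averaged band power as non-phase-locked activity, but it is total power, so an ERP change inside the analysed band and window can shift the ERD/ERS contrast between settings

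*Combined protocol and SAP*

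**What the plan says.** The EEG paragraph under Data Analysis sets out two readouts of the same trial events. The first is the ERP: "We will analyze event-related potentials (ERP) to trial events in individual tasks to investigate phase-locked activity". The second is event-locked power: "Non-phase-locked activity will be investigated by averaging power within alpha, beta, and gamma frequency bands with respect to the trial events". The paragraph then says what the second is for: "The latter analysis technique will permit identification of event-related desynchronizations (ERD) and synchronizations (ERS"), under stimulation settings other than the clinical ones. The comparison it serves is in Aim 3: "We will also collect scalp EEG data during task performance when stimulation is OFF compared to alternative DBS settings".

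That paragraph is the only EEG analysis text. It describes no ERP subtraction, no inter-trial variance method, no split of power into evoked and induced parts, no band limits in Hz and no baseline window. The ERD/ERS sentence cites reference 24. The reference list in the document ends at 12, so the cited method cannot be consulted.

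**The concern.** The two readouts are presented as if they divide the signal between them, with the ERP holding the phase-locked part and averaged power the rest. They do not. Squaring each trial and then averaging keeps everything that is the same on every trial, so the second readout contains the first.

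What is at stake is the interpretation of Aim 3. If a setting enlarges or shrinks an ERP component that lies in an analysed band, the power contrast with OFF moves as well. A change in the evoked response could then be described as desynchronisation or synchronisation of ongoing activity, and one effect could appear in the report under two names. The behavioural analyses for Aims 1 and 2 are not touched.

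**Working it through.** **Inputs.** From the documents: the two readouts, the three bands, the OFF-versus-setting contrast, and the absence of an ERP-removal step. The documents give no EEG figure to reproduce. All amplitudes, waveforms, band limits, windows and trial counts below are assumptions.

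**Step 1, the identity.** Write the band-filtered signal on trial k as x_k(t) = s(t) + n_k(t), where s is the ERP and n_k has mean zero across trials. Then

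E[x_k²] = s² + E[n_k²], that is, total = phase-locked + non-phase-locked.

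This is algebra and needs no simulation. The first term is zero only if the filtered ERP is zero in the window.

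**Step 2, size of the shift between settings.** Let f be the ERP's share of event-window power. If its amplitude is multiplied by r and nothing else changes, total power changes by the fraction f(r² − 1). With f = 0.2 and r = 0.7 this is 0.2 × (0.49 − 1) = −0.10.

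**Step 3, a two-peaked sharp ERP on a realistic background.** Assumed: 2000 trials at 500 Hz; 10 µV rms 1/f background plus a 5 µV rms 10 Hz rhythm of random phase; ERP peaks with SD 20 to 25 ms; alpha 8–12, beta 13–30 and gamma 30–80 Hz. Non-phase-locked activity is identical in every row. Entries are percentage change from baseline.

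| ERP peak (µV) | alpha, total | alpha, ERP subtracted | beta, total | beta, ERP subtracted | gamma, total |
|---|---|---|---|---|---|
| 0 | −0.1 | −0.1 | +0.6 | +0.6 | −0.7 |
| 2.5 | +0.4 | −0.1 | +0.6 | +0.6 | −0.7 |
| 5 | +1.8 | −0.1 | +1.0 | +0.6 | −0.7 |
| 10 | +7.1 | −0.1 | +2.4 | +0.6 | −0.7 |

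The 0 µV row is simulation noise. If a setting halves the ERP from 10 to 5 µV, total alpha power changes by 1.018/1.071 − 1 = −5%. The formula agrees: f = 0.071/1.071 = 0.066, and 0.066 × (0.25 − 1) = −5%. Gamma does not move.

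**Step 4, a slow ERP.** On the same background, a P3-like wave with SD 100 ms left total power the same at 0, 2.5, 5 and 10 µV: alpha +1.1%, beta −0.7%, gamma −0.1% throughout.

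**Step 5, a burst in the centre of the band.** Assumed: 8–12 Hz noise with SD 1, 100 trials, and a 10 Hz phase-locked burst. Total alpha power rose by 28.4, 18.5, 9.7 and 4.0% at amplitudes 1.0, 0.8, 0.6 and 0.4. With the ERP subtracted the readings were +0.7, +0.6, −0.2 and −0.2%. Other burst lengths at amplitude 1.0 gave about +17% to +33%.

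A fall in amplitude from 1.0 to 0.6 is 28.4 − 9.7 = 18.7 points of baseline power. Relative to the larger-ERP setting it is 1.097/1.284 − 1 = −15%. The formula gives f = 0.284/1.284 = 0.22 and 0.22 × (0.36 − 1) = −14%. The two scales should not be mixed.

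**Step 6, direction.** In the additive model the ERP only adds power. Within a setting it therefore gives false synchronisation or masks desynchronisation. A false drop arises only between settings, when the ERP shrinks.

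**Step 7, limits of subtraction.** If the ERP arises because an ongoing rhythm aligns its phase to the event, total power hardly changes and subtraction removes part of a rhythm whose amplitude is unchanged. With moderate alignment (von Mises κ of 1 and 2), total power read about +4%, against about +3% with no alignment, while the subtracted measure read −16% and −43%.

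**The case against.** The strongest reply is that the EEG part of Aim 3 is descriptive. It has no EEG hypothesis and no decision rule, the plan is brief, and the cited ERD/ERS method may include ERP removal. The analysis can also be corrected later on stored EEG. All of that is fair and limits the weight of the point, but it does not repair the sentence: a reader following the text would compute total power and give it the wrong name.

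A reader might infer that any setting that alters the ERP must produce a false desynchronisation or synchronisation. The documents do not support this. They give no ERP waveform, and the effect needs ERP energy inside the band and window. Slow components left all three bands alone, and gamma was unaffected for both ERP shapes tested there. Single smooth deflections of SD 25, 50 and 100 ms, as large as the background SD, changed alpha by only +1.4, −0.5 and −0.9%, which is close to or within simulation noise.

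A reader might also take 28%, or a drop of about 19 points, as the expected bias in this trial. Those figures come from a burst placed at the centre of the band, as large as the background SD. They are near a worst case and depend on the assumed burst length. Nor does the plan say that it will report two separate mechanisms; that is a possible misreading of its results.

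The objection that ERP subtraction should not become the sole readout stands in full, because of the phase-alignment result in step 7.

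**Conclusion.** The point holds in this form: averaged band power as described is total power, it is named as non-phase-locked activity, and no stated step separates the two. An ERP difference between settings can therefore appear as an ERD/ERS difference, mainly in alpha and low beta. The mislabelling is certain; the size is not. Under the assumptions above it runs from about 0 for slow ERPs, through roughly 5 to 7% in alpha for a large sharp ERP, to about 20 to 30% for an in-band 10 Hz burst as large as the background SD. The size rests on an additive ERP and on assumed waveforms, amplitudes, bands and windows. The matter should be settled before the Aim 3 EEG contrasts are interpreted.

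**What to change.** Reword the EEG paragraph along these lines: *Event-locked average band power will be reported as total power. Power will also be computed after subtracting from each trial the average ERP for the same patient, setting, task and trial type, scaled by K/(K − 1) for K trials. Both will be shown beside the ERP. A difference in ERD or ERS between settings will be attributed to non-phase-locked activity only if it is present in the ERP-subtracted measure and is not explained by phase alignment, that is, by subtracted power falling while total power is unchanged.* The paragraph should also state the band limits, event windows and baseline, since the size of the effect depends on them.

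The cost is one extra preprocessing step and a second set of results, with no additional patients, visits or recordings. Two limits should be stated with it. Trial-to-trial variation in ERP size or latency leaves a small residual leak after subtraction. Phase alignment of ongoing rhythms can lower the subtracted measure without true desynchronisation, so neither measure should be read alone.

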6. Hearing or visual impairment precluding cognitive testing

Exclusion criteria for Imaging procedures is not applicable. Healthy controls will only complete EEG monitoring and cognitive testing.

Research Procedures – Arm 1 (12 patients)

Study Day 1: Patients will be admitted to the Clinical Research Unit of the Clinical and Translational Research Center on Study Day 1 after withholding Parkinson's medications overnight. After admission, they will undergo initial stimulation threshold evaluation (for sensorimotor stimulation side effects) with a physician's assistant trained in DBS programming. An EEG technician will apply scalp electrodes and electroencephalogram (EEG) activity will be monitored throughout the Study visit using standard electrophysiological equipment under the supervision of Dr. _____. Subjects will then complete two test sessions, at different stimulation parameters (varying contacts and frequencies designed by Dr. _____ at Case Western Reserve University) at the amplitude corresponding to 90% of side effect threshold.

Test sessions: Each testing session involves performance of several tasks including a phonemic fluency, semantic fluency, Simon task, Facial Affect Recognition task (FAR), Time Production task, Interval Judgment task, as well as a speeded finger tapping test and a group of visual analogue rating scales regarding current mood and well-being (anxiety, motivation, fatigue, physical discomfort).

There will be at least 30 minutes between each session for wash-in/washout of stimulation effects and to rest. Patients will be provided with lunch and additional rest breaks, as needed. At the end

of the last session, patients will take their regular PD medications and stimulation will be readjusted to their clinically-defined settings. Note that STN DBS therapy has a 'wash-in' period of seconds to minutes, while medication therapy typically has a 'wash-in' period of around 15 to 30 minutes. EEG electrodes will be removed and they will be discharged from the CRU when the patient subjectively feels that their stimulation therapy and medications have taken effect, and the supervising neurologist or movement disorder Physician's Assistant delegate observe that Parkinsonian symptoms have improved.

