Patient-specific stimulation settings: Deidentified pre- and post-operative imaging will be shared with Dr. _____ at Case Western Reserve University for creation of patient-specific stimulation parameters (Data Use Agreement attached). Patient specific stimulation models for the active cathode/anode that preferentially activate dorsal and ventral aspects of the Subthalamic Nuclei will be constructed prior to the patients' arrival. All stimulation adjustments will be completed by an unblinded Physician Assistant trained in DBS programming. Patients will be blinded to stimulator settings and all data collection will be completed by blinded study personnel. We recognize that it is likely not possible to complete the research sessions for DBS patients in a fully blinded manner: in particular, the off-stimulation state and the low frequency stimulation states may be obvious to both patients and study personnel in the absence of medications. At each session, we will assess patient blinding (i.e., query patients' belief regarding current stimulator setting) to identify those patients who remain blinded for possible subgroup analyses.

Study Day 2: On a second day (scheduled at the subjects' convenience, within 4 weeks of the first study day), patients will again be admitted to the Clinical Research Unit of the Clinical and Translational Research Center after withholding Parkinson's medications overnight. After admission, an EEG technician will apply scalp electrodes and electroencephalogram (EEG) activity from the Epilepsy Monitoring Unit, under the supervision of Dr. _____. Subjects will then complete the three remaining test sessions at different stimulation parameters (varying contacts and frequencies designed by Dr. _____ at the Case Western Reserve University) at the amplitude corresponding to 90% of side effect threshold.

ARM 1

Day 1 Clinical Research Unit

Start Time Minutes Procedure

7:00	15	Informed Consent and Admit to CRU
7:15	60	EEG leads applied
8:15	15	Threshold Evaluation
8:30	30	Setting 1 and wash-in
9:00	30	Test Session 1
9:30	30	Setting 2 and wash-in
10:00	30	Test Session 2
10:30	60	Meds resumed, Clinical settings applied, EEG leads removed, and discharge

Day 2 Clinical Research Unit

Start Time Minutes Procedure

7:00	60	EEG leads applied and admit to CRU
8:00	30	Setting 3 and wash-in
8:30	30	Test Session 3
9:00	30	Setting 4 initiated
9:30	30	Test Session 4
10:00	30	Setting 5 initiated
10:30	30	Test Session 5

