A Data Monitoring Committee is not planned for this study. The Principal and Co-Investigators, as well as other protections in place (i.e., CRU clinical staff), will continuously monitor subject safety and data integrity. Adverse events and Unanticipated Problems will be reviewed by the Principle and Co-Investigators. If an Adverse Event occurs, it will be recorded on the Adverse Event Summary Sheet, and this will be submitted along with the Adverse Event Report in accordance with the stated time limitations. No clinical electrophysiological report will be generated as the recordings performed do not constitute diagnostic studies. However, if an unexpected finding is observed during the electrophysiological analysis (e.g., seizure activity), consult to the Epilepsy Center will be ordered. Likewise, if an unexpected finding is observed during the MRI procedure (e.g., mass), Dr. _____ will consult with the patient.

Consent

The informed consent process for controls will be completed on the study day prior to EEG electrode application by Dr. _____ or the research coordinator. The informed consent process for patients will be completed by Dr. _____ or the research coordinator/technician in a 2-step process.

Step 1:

For patients approached during a regularly scheduled clinical visit to CCF Main campus: The full procedures, risks, benefits, and alternatives to participation will be reviewed with patients in a private setting (i.e., exam room). Potential participants will be given a copy of the full written consent document (either with or without Study Day 3, depending on the type of DBS system implanted) and are given the opportunity to review the document and ask questions or clarifications of the person conducting the consent interview. The patient is also permitted to discuss the matter with their spouse/caregiver privately before consenting to participate. Patients who wish to proceed will provide limited written consent to access their neuroimaging data obtained as part of routine clinical care for pre-surgical planning and post-operative electrode placement confirmation, de-identify those scans, and deliver them in encrypted format to Dr. _____ for creation of patient-specific stimulation parameters.

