For patients not seen in clinic: A letter will be mailed to potential subjects (see Recruitment letter), which includes the screening consent and the main study consent. Study personnel will conduct a follow up phone call (See Screening Telephone Script) to ensure that patients received the letter and to review the main study and the initial screening consent. If the patient agrees to participate, he/she will be asked to sign the screening consent and return it via the self-addressed and stamped envelope provided in the mailing. Upon receipt of the signed screening consent, de-identified scans will be transmitted to Dr. _____ at CWRU. The appropriate confirmation letter (see Confirmation letters – ScreenIn or ScreenFail) will be sent to patient to inform them of whether personalized stimulation models could or could not be constructed. For those patients who screen in, there will be a follow up phone call to serve as the main study consent discussion (See Consent Telephone Script) and to schedule an appointment at the CRU, if the patient provides verbal consent to participate).

Step 2:

Patients will be consented with the full informed consent process when they arrive at the CRU for the first Study Day. The consent process will take place in a private CRU inpatient room.

When patients return for additional study sessions, they will be reminded, before study procedures commence, that they may withdraw consent at any time without consequences.

References

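### Written main-study consent for the 12 Arm 1 patients comes after their first study-required overnight withholding of Parkinson's medication

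*Combined protocol and SAP*

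**What the plan says.** The Consent section sets out a two-step process for patients.

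- **Step 1, patients seen in clinic.** Procedures, risks, benefits and alternatives are reviewed in private. The patient receives the full consent form, can ask questions and can talk with family. Those who want to go on then give "limited written consent to access their neuroimaging data obtained as part of routine clinical care", which extends to de-identifying the scans and sending them for stimulation modelling.
- **Step 1, patients not seen in clinic.** They are mailed a letter "which includes the screening consent and the main study consent", and a telephone call reviews both. They sign and return the screening consent, which triggers transfer of the scans. Patients for whom a model can be built get a second call. It serves as the main-study consent discussion, and a visit is booked if they agree verbally.
- **Step 2, all patients.** "Patients will be consented with the full informed consent process when they arrive at the CRU for the first Study Day".

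The Arm 1 schedule agrees with Step 2: its opening Day 1 entry, at 7:00 for 15 minutes, is "Informed Consent and Admit to CRU". The Arm 1 procedures text has patients admitted "on Study Day 1 after withholding Parkinson's medications overnight". Arm 2 patients are tested on their regular medication.

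**The concern.** The overnight withholding is done for the study. No clinical reason is given for it, and Arm 2, drawn from the same kind of patient, does without it. It is therefore a study procedure, and for Arm 1 it takes place at home the night before the only signature described as covering the main study.

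At stake is patient protection. A patient who declines at 7:00 has already gone without medication for a study not joined in writing. A patient who accepts signs while unmedicated, after travelling in, in a 15-minute slot shared with admission. If a problem arose overnight, the site would hold no signed main-study consent covering the change that led to it.

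**Working it through.** No formula applies and the plan gives no figure to reproduce. The check is the order of events in Arm 1, from the Consent section, the Arm 1 procedures text and the Arm 1 schedule.

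| Order | Event | Consent held at that point |
|---|---|---|
| 1 | Step 1 review; main form given or mailed | Written: scan use (clinic) or screening (mail) |
| 2 | Mail route: second call after screening in | As above, plus verbal agreement to the main study |
| 3 | Night before Day 1: medication withheld | As above |
| 4 | Day 1, 7:00: full consent and admission | Written main-study consent |
| 5 | 7:15 EEG leads; 8:15 threshold evaluation; 8:30 first setting; 9:00 first test session | Written main-study consent |

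Event 3 precedes event 4. No section describes a written main-study consent before event 3. For clinic patients, no explicit agreement to the main study is described between the Step 1 review and arrival, beyond their wish to proceed.

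**Who is affected.** The arm heading, "Research Procedures – Arm 1 (12 patients", gives 12. With 3 in Arm 2, the share is 12 / (12 + 3) = 12/15 = 80% of patients. The plan does not say how many come by each route, so the 12 cannot be divided between scan-only and screening-plus-verbal consent.

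**Who is not affected.** Arm 2 stays on medication. Controls withhold nothing and consent before electrodes are applied. Arm 1 patients withhold again before Day 2 and, where they are scanned, before Day 3, but those nights follow the Day 1 signature. The gap is one night per Arm 1 patient.

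**Are data affected?** Every Day 1 procedure is scheduled at 7:15 or later, after the consent slot ends. The only earlier data use is of existing clinical scans, which has its own written consent.

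**Is a risk stated?** Not for withholding alone. The Adverse Events and Safety section expects temporary worsening from non-clinical or absent stimulation, and that begins only after consent. A symptom burden from withholding can be inferred from two places. Discharge from Day 1 waits until medication and stimulation have taken effect and staff see improvement. The paragraph on patient-specific settings expects some stimulation states to be recognisable because patients are unmedicated. Nothing says that stimulation is changed before arrival, so clinical settings presumably run overnight and may soften the effect.

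**Does the plan follow another order elsewhere?** Yes. Controls consent before the first procedure, and returning patients are reminded of their right to withdraw before procedures start. Arm 1's first night of withholding is the exception.

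**The case against.** The best defence is that this is a deliberate two-step design that informs patients well. Clinic patients have the full review and the form in hand, with time to discuss it. Mail patients have two telephone discussions and must agree verbally before a visit is booked. Eligibility requires ability to consent and excludes dementia. Much of this stands, and it rules out four stronger readings that a reader might infer:

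- **That the sections contradict each other.** They do not. The procedures text, the schedule and both consent steps fit one consistent sequence. The issue is the sequence chosen.
- **That the Arm 1 data are compromised.** No mechanism supports this, since all Day 1 measurements follow consent and the scans are separately covered.
- **That patients are uninformed, or cannot validly consent off medication.** The prior review answers the first, and nothing in the documents suggests the second.
- **That the plan acknowledges a hazard from overnight withholding.** It names worsening only for stimulation changes.

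It is also fair to say that the consent forms, telephone scripts and confirmation letters are not in the available text. The screening consent used in the mail route might already mention withholding; its scope is not defined there. In the clinic route the description is narrower and points the other way.

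The defence does not supply a written main-study consent before the first withholding. Prior information and, for some patients, verbal agreement reduce the gap but do not document consent.

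**Conclusion.** The point holds as a gap in documented consent. As written, all 12 planned Arm 1 patients (80% of the 15) undergo one study-required overnight withholding before the full consent process. It is a modest, cheaply corrected weakness in patient protection, with no consequence for the data or the analysis.

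The conclusion rests on three assumptions: that the withholding is for the study and not part of usual care, which the contrast with Arm 2 supports; that the earlier forms cover no more than the Consent section describes, which could not be checked; and that withholding carries some symptom burden, which is inferred from the discharge rule and the remark on unmedicated patients. If an earlier signed form already covers withholding, only a clarification is needed.

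**What to change.** Amend the Consent section so that written main-study consent is obtained before the first overnight withholding:

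- **Clinic route:** sign the full form at the Step 1 review, where it is already handed over and discussed.
- **Mail route:** sign and return the main form, already in the mailing, after screening in and after the existing consent call.
- **Day 1, 7:00:** use the slot to reconfirm willingness and answer questions.
- **If an existing form already covers withholding:** name it in the Consent section and say so.

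The medication rule is outside this point and stays as written.

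The cost is wording and script changes, an IRB amendment and return postage for the mailed form. Some clinic patients will sign and later fail screening because no stimulation model can be built for them; mail patients avoid this, since they would sign only after screening in. No additional visit or call is needed if clinic patients sign at Step 1. Putting their signature off to a later date would need a contact that the plan does not now describe.
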